1) **Title:** The Effect of oral PhenazopyrIdine on Perioperative voiding After mid-urethral sliNg (EPIPhANy study)

2) IRB Review History*

N/A

3) Objectives*

- a) Primary objective: Evaluate the effect of phenazopyridine (brand name Pyridium) on immediate postoperative voiding function in patients undergoing midurethral slings
- b) Secondary objective: Evaluate percent pain reduction with and without use of oral Pyridium at two hours post-procedure.

4) Background*

The midurethral sling (MUS) is a very common, highly successful procedure for the management of stress urinary incontinence due to urethral mobility, with cure rates ranging from 80 to 86%. A common complication of the MUS procedure is short-term postoperative voiding dysfunction. Approximately 20% (7) of patients undergoing MUS are unable to void in the immediate postoperative period and are discharged home with indwelling bladder catheter for 3-5 days. Virtually all patients discharged with a catheter are able to effectively void within 5 days of the procedure and long-term voiding dysfunction is extremely uncommon

A secondary analysis of a recent study at UMass examining the effect of local anesthetic on postop voiding function showed a potentially dramatic effect of oral phenazopyridine on reducing postoperative voiding dysfunction. During the study, a medication used to dye the urine blue to assess for ureteral injury became briefly unavailable commercially. As a result, we preoperatively gave all patients Pyridium because it has the side effect of dying the urine orange. This allowed us to evaluate the flow from the ureters if needed. This transition occurred in the middle of the study and at the conclusion, we observed that the rate of voiding dysfunction decreased from approximately 28% in those not receiving pyridium to 10% in those receiving pyridium. Because the study was not designed to study this serendipitous finding, we propose to formally assess the validity of this observation. Other than our study, there are no other publications that demonstrate that phenazopyridine may have an effect on postoperative short-term voiding dysfunction. At this time there is no evidence of adverse effect to denying patients phenazopyridine. Because of the nature of our surgical practice, many of the procedures we perform have the risk of ureteral injury and we made a decision to give this medication preoperatively to all of our patients. In the 15 years that the PI has practiced, we have never seen a ureteral injury in a patient undergoing a midurethral sling. The documented risk of injury to the lower urinary

Page 1 of 10

tract during anti-incontinence surgery is approximately 2.6%, with all of these injuries being to the bladder or urethra and 0 ureteral injuries in 351 cases. There is no place for phenazopyridine in the management or assessment of injuries to the bladder or urethra and many providers at UMass and other institutions in the US do not give phenazopyridine to their patients undergoing a midurethral sling. Phenazopyridine is the only oral medication that is available to evaluate the patency of the ureter after pelvic surgery.

References:

- 2. Nilson CG Kuuva N, Falconer C, Rezapour M, Ulmsten U, (2001) Long term results of he tension-free vaginal tape (TVT) procedure for the vaginal treatment of female stress incontinence. Int Urogynecol J Pelvic Floor Dysfunct 12(Supple. 2): S5-8.
- 3. Voiding function after Mid-Urethral Slings with and without local anesthetic: Randomized Controlled Trial. UMass IRB H-14197

5) Inclusion and Exclusion Criteria*

Inclusion criteria:

1. Any female subjects scheduled to undergo Mid-Urethral Sling (MUS) through the UMass urogynecology service for incontinence.

Exclusion criteria:

- 1. Planned concurrent prolapse or other procedure besides cystoscopy
- 2. Using intermittent self catheterization preoperatively
- 3. Undergoing spinal anesthesia for the procedure
- 4. Known allergy to phenazopyridine (AKA Pyridium)
- 5. Renal insufficiency
- 6. Any condition or situation that in the attending physician's opinion would contra-indicate the use of phenazopyridine
- 7. Subjects not competent to give consent
- 8. Prisoners
- 9. Non-English or non-Spanish speaking patients
- 10. Age < 18
- 11. Pregnant patients
- 12. Contraindications to the use of IV methylene blue including
 - a) Patients with known hypersensitivity reactions

Page 2 of 10 Revised: 6/30/16 Approved 7/7/16

- b) Severe renal insufficiency
- c) Patients with G6PD deficiency

6) Study-Wide number of Subjects*

N/A not a multicenter study

7) Study-Wide Recruitment Methods*

N/A not a multicenter study

8) Study Timelines*

- Participants will be enrolled in the study for approximately 6 weeks.
- We anticipate 2 years to enroll all the subjects into the study
- Primary analysis will be completed within 6 months after enrollment is completed.

9) Study Endpoints*

- Primary outcome is the rate of voiding dysfunction between the two groups.
- Secondary outcomes include: complications, perioperative pain scores,
- Once 50% of the subjects have completed their procedures, we will perform an interim analysis of the rates of voiding dysfunction. If there is a statistically significant difference (p<0.01) at this interval analysis, we will terminate the study.

10) Procedures Involved*

Study design and randomization

This study is a randomized controlled trial. Randomization will be performed using software and a block randomization scheme. Study assignment will be completed using sequentially numbered sealed opaque envelopes. All the research procedures described other than the use or not of phenazopyridine will be applicable to both arms of the study. Subjects will have a 50% chances of getting either phenazopyridine or nothing.

Because pyridium turns the urine orange, it is impossible to blind the patients and researchers to the study assignment. Because there is no known placebo that turns the urine orange, there is no value to using an actual placebo tablet. Subjects will be assigned to either receive pyridium or not receive pyridium preoperatively.

Page 3 of 10 Revised: 6/30/16 Approved 7/7/16

Screening potential subjects: Investigators will screen potential subjects for contraindications to methylene blue. Prior obtaining the routine surgical consent for the potential subject's surgical procedure, the patient's medical history in the UMass Electronic Medical Record is routinely reviewed. The medical record will be reviewed for a diagnosis of G6PD and if found, the potential subject will be excluded.

Once written consent has been obtained, subject number will be assigned and the appropriate randomization envelope will be opened. The study assignment will not be formally shared with the subject. Those assigned to the "pyridium" arm will have orders written for the standard 200 mg dose of pyridium to be given on arrival to the Surgical Admissions Care Unit (SACU). Those assigned to the "NO pyridium" arm with have their routine preoperative orders written along with an order for "No preoperative pyridium".

Subjects will then follow the routine perioperative care for their procedures with the only study interventions being the gathering of PHI and performing postoperative pain assessments.

PHI will be obtained at the time of the surgical consent with the purpose to evaluate for possible confounders affecting the postoperative bladder function.

Surgical procedure:

The Mid Urethral Sling will be performed in standard fashion based on manufacturer's recommendations and instructions to minimize inter-observer variations. We will perform the procedure according to our usual and customary techniques. The subject will receive the same technique and interventions that a routine patient on the Urogyn service would expect to undergo. There will be no changes to the technique for the purpose of the study.

Bladder challenge:

Patient will undergo voiding trial at same day surgery per our usual and customary protocol. This is the same protocol the subject would undergo as a patient on the Urogyn service. The bladder challenge will be interpreted in our usual manner and the subject managed according to our routine clinical protocols.

Postoperative care:

Subjects will undergo routine postoperative care and followup. Subjects failing their bladder challenge will be seen in the Urogyn clinic according to routine clinical protocols and data councerning their void trials collected. Subjects will undergo routine followup evaluation 6 weeks postoperatively in the order to assess any potential long-term voiding dysfunction. Information on any postoperative complications will be collected

Administration of Visual analog scale:

Page 4 of 10 Revised: 6/30/16 Approved 7/7/16

- (1) Visual analog scale for assessment of pain will be administered at two time intervals.
 - (a) VAS #1) Preoperative VAS will be done by the principal investigator or any of the study assistants. The VAS form will be part of subject's packet.
 - (b) **VAS#2)** VAS will be administered by one of the study investigators 2 to 3 hours after the surgical procedure in the SACU.

11) Data and Specimen Banking*

N/A

12) Data Management*

Power Calculation: We used data from the recent "*Urine and Me*" study conducted at UMass. A 20% percent difference in subjects passing the bladder challenge was felt to be clinically significant. In order to capture this difference a power calculation was performed via the Wilcoxon signed-rank test. Based on this, to detect a 20% difference with a α -error = 0.05 and a power (1- β error) = 0.80, a minimum of 41 subjects per group (82 total) will need to be recruited. Assuming ~ 10% dropout rate (8), we will seek to recruit 90 patients.

Data analysis: Continuous measures will be compared using the unpaired Student's t test. Association between outcome measures and graph assignment will be adjusted according to demographic differences using an analysis of covariance. Standard statistical programs (SAS, SPSS) will be used to determine the mean differences between the voided/catheterize and bladder scanner volumes.

13) Provisions to Monitor the Data to Ensure the Safety of Subjects*

There is minimal risk involved with the denial of pyridium to subjects. Prior to the withdrawal of indigo carmine from the market in 2014, patients did not routinely receive pyridium preoperatively. Currently a minority of surgeons use pyridium in sling procedures with most using nothing. In the event that the ureters need to be assessed for patency, subjects will be given methylene blue to dye the urine. This is the intervention currently used to assess ureters in procedures where ureteral patency is assessed. Thus both groups are receiving care that is considered within the standard of care.

Subjects will be monitored in a similar manner to all of our postoperative patients. There is a chance that pyridium may be beneficial to patients and that denying this medication may result in less desirable outcomes. This study is specifically designed to look at the issue. We plan to perform an interim analysis of the data once 50% of subjects have completed the study and if there is a clear benefit (or harm) from this medication, will terminate the study early and offer the medication to all patients.

Page 5 of 10 Revised: 6/30/16 Approved 7/7/16

14) Withdrawal of Subjects*

Subjects are free with withdraw from the study at any time. If subjects withdraw their participation, any data that has already been collected for research purposes will be destroyed or anonymized so that it can no longer be identified with the subject. There should not be additional data collection of demographic information for research purposes at the time a subject withdraws their consent for the study.

15) Risks to Subjects*

This study poses minimal risk to subjects. Subjects randomized to the pyridium arm will receive pyridium as it is commonly given to patients undergoing reconstructive procedures currently through the Urogyn division at UMass. Subjects denied pyridium will undergo the same procedures and techniques that our patients not in the study will receive.

One risk from the study is the risk associated with denying subjects preoperative pyridium for their procedure. Because pyridium is used to dye the urine for evaluation of the ureters, in the event there is concern for ureteral injury, patients will be given methylene blue to dye the urine. In addition over the last 5 years and over 300 cases at UMass, there have been no cases where there has been concern for ureteral injury at the time of a midurethral sling placement. In patients undergoing gyn procedures where injury to the ureter is suspected, methylene blue is routinely given to evaluate for ureteral patency. Thus the patients in both arms will be receiving care that is considered standard for these procedures.

Investigators will screen potential subjects for contraindications to methylene blue. Prior obtaining the routine surgical consent for the potential subject's surgical procedure, the patient's medical history in the UMass Electronic Medical Record is routinely reviewed. The medical record will be reviewed for a diagnosis of G6PD and if found, the potential subject will be excluded.

There is a risk of unauthorized disclosure of protected health information. The datasheets will be kept in a locked cabinet in a locked office in the administrative offices of the division on Jaquith 2. The data will be entered into a de-identified, password protected file kept on the departmental computer servers.

16) Potential Benefits to Subjects*

Subjects who receive pyridium may have a lower rate of perioperative voiding dysfunction and a lower rate of perioperative catheterization.

Page 6 of 10 Revised: 6/30/16 Approved 7/7/16

17) Vulnerable populations

N/A

18) Multi-Site Research*

N/A

19) Community-Based Participatory Research*

N/A.

20) Sharing of Results with Subjects*

N/A.

21) Setting

Subjects will be identified and recruited at the urogynecology clinic located at UMass Memorial and the urogynecology clinic at Westborough UMass Memorial Health Care. The urogynecology division has two full time designated surgeons (the PI is one of them) and both will be part of the study. In addition one urogynecology fellow will work as a study assistant. All these three members will participate recruiting subjects and obtaining intraoperative and postoperative data.

There will be no composition or involvement of any community advisory board, and this research will not be conducted outside of UMass or its affiliates.

22) Resources Available

This research will be conducted through the scheduled urogynecology clinic.

Roles of the members of the study:

- Principal investigator. Identifying potential subjects for the study, consenting of subjects, performing surgical procedures, participating in the data analysis, preparing submissions to the IRB, oversight of the conduct of the study and research personnel.
- Study assistants. Identifying potential subjects for the study, consenting of subjects, assisting in the surgical procedures.
- Biostatistician. The OBGYN Department has a designated biostatistician who will help with the data analysis. The biostatistician will not participate in the recruitment of study subjects.

The PI, co-investigator and all study assistants are CITI-trained. All of them are also clinical members of the urogynecology division at UMass Memorial Medical Center Department of Obstetrics and Gynecology. Before initiation of the research, all study assistants will be instructed on

Page 7 of 10 Revised: 6/30/16 Approved 7/7/16

the protocol and research procedures at the urogynecology department's scheduled bimonthly research meetings.

23) Prior Approvals

N/A

24) Recruitment Methods

Subjects will be recruited through the outpatient Urogynecology clinics of the Urogyn faculty. Patients scheduled to undergo a midurethral slings and meeting criteria will be approached for participation when they present for their preoperative evaluation.

Investigators will screen potential subjects for inclusion and exclusion criteria to the study including contraindications to methylene blue. Prior obtaining the routine surgical consent for the potential subject's surgical procedure, the patient's medical history in the UMass Electronic Medical Record is routinely reviewed. The medical record will be reviewed for a diagnosis of G6PD and if found, the potential subject will be excluded.

Potential subjects will be approached by their surgeon at their preoperative visit. Once eligibility has been confirmed, potential subjects will be offered the opportunity to participate in the study. The study will be reviewed in detail and ample opportunity for questions will be given. The opportunity to decline participation will also be given. For women agreeing to participation, informed written consent will be obtained.

25) Local Number of Subjects

90 subjects will be enrolled in the study.

26) Confidentiality

Data on participants will be stored under a participant ID number to ensure confidentiality. This data will be stored initially in a locked filing cabinet until it can be transcribed into the redcap database which will be password protected on the protected redcap server. The database will be a deidentified database. Data will be stored for seven years.

Data security. De-identified subject data will be stored in locked filing cabinet in the locked office of the PI. A study key will be maintained linking study numbers to subject identifiers. This dataset will be entered in a computer database which will be stored on a firewall protected, password-protected computer of the PI in a locked office. The subject ID and source documents will be stored in a locked cabinet in the PI office. Personal identifiers will be destroyed at the earliest opportunity, no later than completion of the study.

Page 8 of 10 Revised: 6/30/16 Approved 7/7/16

27) Provisions to Protect the Privacy Interests of Subjects (HIPAA)

Participants will be asked to sign a HIPAA authorization. The data collected on participants will be stored in a locked filing cabinet in the locked office of the primary investigator. Only the primary investigator and a co-investigators will have access to it. To further ensure confidentiality, all data will be stored under assigned study ID numbers rather than personal identifiers such as name or medical record number.

28) Compensation for Research-Related Injury

Because this is minimal risk, there will be no compensation for subjects participating in the study. In the unlikely event of research-related injury, no funds have been set aside and the study subject will be responsible for cost of care of any research related injury.

29) Economic Burden to Subjects

There is no economic burden to the subjects. Both groups are receiving care that is considered within the standard of care and all examinations, interventions and procedures will be occurring regardless of the subject's participation in the study. The pyridium is administered as part of a global fee for the surgical procedure and there is no charge to the patient or her insurance for this medication. Because phenazopyridine is a low cost generic medication, its cost compared to the cost of the surgical procedure is negligible to the medical center.

30) Consent Process

The PI and study staff will follow the UMMS Investigator Guidance for Informed Consent (HRP-802). Subjects who agree to participate will be consented per SOP at Urogynecology clinic by the attending performing the mid urethral sling procedure. Patients will be given ample time to decide and after written and verbal consent is given they will be told they can withdraw from study at anytime despite consenting for the study. Additionally, subjects will be encouraged to ask additional questions regarding the study and their participation. A copy of the consent will be provided with the principal investigator number. Subjects will be encouraged to call with any additional questions.

Non-English Speaking Subjects

Spanish speakers will be invited to the study. A Spanish consent translated from the English version will be used (attachment 8). [name] and [name], who is a co-investigators, are native Spanish speakers, and

developed the Spanish versions of the consents and summary (Attachment #9). Only [name] and [name] will be recruiting Spanish speaking subjects following the same steps as above employed for English speakers.

31) Process to Document Consent in Writing

The PI and study staff will follow the UMMS Investigator Guidance for Documentation of Informed Consent (HRP-803)

32) Drugs or Devices

Phenazopyridine is a lawfully marketed drug in the United States. The medication is IND exempt based on the following categories:

This medication is considered within the standard of care for the assessment of ureters after an urogynecologic procedure, including midurethral slings. The medication will be orally administered and does not involve a route that increases the risk associated with the use of the product.

This investigation is not intended to be reported to FDA as a well-controlled study in support of a new indication for use nor intended to be used to support any other significant change in the labeling for the drug.

This investigation is not intended to support a significant change in the advertising for the product.

Page 10 of 10 Revised: 6/30/16 Approved 7/7/16

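### Minor, secondary endpoint: the pain objective names a percentage with no formula; define one pain variable, the postoperative VAS adjusted for the preoperative VAS already collected

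*Combined protocol and SAP*

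**What the plan says.** Four sections of the combined protocol and SAP bear on pain.

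- **Section 3 (Objectives), item b:** "Evaluate percent pain reduction with and without use of oral Pyridium at two hours post-procedure". It gives no formula or denominator, and does not say whether the percentage is formed per subject or between arms.
- **Section 9 (Study Endpoints):** "Secondary outcomes include: complications, perioperative pain scores". These are scores, not percentages, and no time point is given.
- **Section 10 (Administration of Visual analog scale):** "Visual analog scale for assessment of pain will be administered at two time intervals". For the first, "Preoperative VAS will be done by the principal investigator or any of the study assistants". For the second, "VAS will be administered by one of the study investigators 2 to 3 hours after the surgical procedure in the SACU".
- **Section 12 (Data analysis):** "Continuous measures will be compared using the unpaired" t test. Associations between outcomes and assignment "will be adjusted according to demographic differences using an analysis of covariance". Neither pain nor the preoperative VAS is named.

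The inclusion criterion in Section 5 is "Any female subjects scheduled to undergo Mid-Urethral Sling (MUS) through the UMass urogynecology service for incontinence". No criterion requires preoperative pain.

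**The concern.** The objective and the endpoint list name different pain variables, and the objective's variable is not defined. A reduction implies a starting value, and the only starting value collected for each subject is the preoperative VAS. Women having a sling for incontinence need not have pain beforehand, so many of those scores could be 0 or close to it. Dividing by them would drop the zero-baseline subjects and let the lowest non-zero baselines dominate the arm means.

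Two separate costs follow. If the analyst commits to the per-subject percentage, power is lost. If the metric stays open until the data are in, the raw score, the change score and the percentage all fit the wording, and choosing among them inflates the false-positive rate. The trial is unblinded (Section 10), which is a further reason to fix the variable in advance.

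**Working it through.** The plan states no sample size, SD, effect or power for pain, so it has no figure to reproduce. The check is therefore arithmetic on the ratio, followed by simulation under assumed inputs.

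**1. The ratio.** Per-subject percent reduction = 100 x (pre - post) / pre.

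- pre 0: division by zero, no value.
- pre 1, post 3: 100 x (1 - 3)/1 = -200%.
- pre 5, post 7: 100 x (5 - 7)/5 = -40%.

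The same 2-point rise differs fivefold by baseline alone.

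**2. The alternative reading.** 100 x (no-pyridium mean - pyridium mean) / no-pyridium mean, from the postoperative scores, divides once by an arm mean. Neither problem arises.

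**3. Simulation inputs.** From the plan: 41 per arm, which Section 12 derives for the voiding outcome. Assumed: postoperative means 40 and 28 of 100 (difference 12), residual SD 20, slope 0.3 on baseline, non-zero baselines 1 plus an exponential with overall mean 10, and 20%, 50% or 80% of baselines at 0. The text does not state the VAS scale, so a 0-100 version and a whole-number 0-10 version were both run, with 4,000 trials per scenario. As a check on the plain t test: 12/20 = 0.6 SD, noncentrality 0.6 x sqrt(41/2) = 2.72, analytic power 76.5%.

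Subjects with no percentage, of 82: 0.2 x 82 = about 16; 0.5 x 82 = 41; 0.8 x 82 = about 66.

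| Baselines | Percent, 0-100 | Percent, 0-10 | Plain t on postoperative VAS |
|---|---|---|---|
| mean 10, no zeros | 24% | 66% | 74-75% |
| mean 10, 20% zeros | 20% | 56% | 74-75% |
| mean 10, 50% zeros | 12% | 37% | 74-75% |
| mean 10, 80% zeros | 6% | 17% | 74-76% |
| near 50 (SD 10), no zeros | 73% | 71% | 75-76% |

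With non-zero baselines averaging 20 or 30 and 20-80% zeros, the percentage has 4-16% power (0-100) or 10-43% (0-10), against 69-75% for the plain t test.

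**4. False positives.** With no true effect, the percentage tested alone rejects in about 3-5% of trials, so a metric fixed in advance is not anti-conservative. The open choice is different. Rejecting if either the percentage or the raw score reaches p<0.05 gives roughly 7-10%. Adding the change score as a third option gives roughly 9-12%.

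**5. ANCOVA on preoperative VAS.** Against the plain t test, the power difference is about nil with baseline mean 10 (for example 75.1% to 75.3% at 50% zeros, 0-100) and up to about 6 points with baseline means of 20 to 30. The gain depends on the assumed correlation between preoperative and postoperative pain.

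**The case against.** The best defence is that the plan already contains a sound analysis. Section 9 names scores, a VAS score is a continuous measure, and Section 12 sends continuous measures to an unpaired t test. No section tells anyone to divide by the preoperative VAS. Section 3 can be read naturally as a contrast between arms at one time. If preoperative pain is near 0, pain will rise after surgery, and a per-subject reduction from that baseline makes little sense. On this view Section 3 is simply loosely worded.

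Most of this stands, and it is why the point is minor. It does not close the matter. The Section 12 sentence fixes the test but not the variable, since a t test applies equally to a raw score, a change or a percentage. The objective still names a quantity that appears nowhere else.

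It is also fair that the power figures rest wholly on assumed inputs. The exponential baseline puts many values near the floor, where the ratio behaves worst, and changing the scale alone moves the no-zeros case from 24% to 66%. The figures show what could happen; they do not estimate this trial's loss.

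A reader might also infer that a preoperative VAS taken after allocation is biased. The plan does not state the order of the two, and no bias is shown. Requiring the score before the envelope is opened could move an assessment to an earlier visit, so no such change is asked for. The gap between two hours in Section 3 and 2 to 3 hours in Section 10 is only a consistency edit.

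**Conclusion.** The point holds as a minor inconsistency on a secondary endpoint. Section 3 names an undefined percentage, one permitted form of which is badly behaved at low baselines, and the planned covariate adjustment omits the preoperative VAS. The arithmetic on the ratio needs no assumptions. The size does: about 6% to 73% power against about 75% in the tabulated scenarios, slightly lower still in some others, and no loss if the percentage is a contrast of arm means.

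Two stronger readings are tempting and unsupported. One is that the plan prescribes a per-subject percentage and will lose most of its power for pain; no section prescribes it, and no VAS data are given. The other is that the pain result will be biased; no such conduct is shown, and the inflation to roughly 7-12% arises only if the metric is chosen after seeing the data. It would be equally wrong to call the cost purely one of precision, because the open wording permits that choice. The primary outcome, sample size and interim rule are unaffected.

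**What to change.** Use one pain variable in Sections 3, 9 and 12: the VAS at 2 to 3 hours after surgery, compared between arms as a mean difference with 95% CI by ANCOVA with preoperative VAS as covariate. Add that covariate to the existing ANCOVA sentence in Section 12. A baseline of 0 is harmless as a covariate, so no subject with both scores is dropped. Report any percentage only descriptively, from arm means as in step 2 of the working. Make the Section 3 time match Section 10.

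The cost is wording in three sections. Both scores are already collected, so no subjects, visits or tests are added. The main benefit over the percentage is a defined, stable measure chosen in advance; any power gain over the plain t test is about nil if baselines sit near 0, and larger if preoperative and postoperative pain are correlated.

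### Sections 9 and 13 give different rules for the same interim look, and the plan's 0.05 makes no allowance for that look

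*Combined protocol and SAP*

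**What the plan says.** Section 9 (Study Endpoints) defines the endpoint: "Primary outcome is the rate of voiding dysfunction between the two groups". It then sets the look: "Once 50% of the subjects have completed their procedures, we will perform an interim analysis of the rates of voiding dysfunction". The rule is: "If there is a statistically significant difference (p<0.01) at this interval analysis, we will terminate the study".

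Section 13 (Provisions to Monitor the Data) describes an interim analysis again: "We plan to perform an interim analysis of the data once 50% of subjects have completed the study". The consequence is that, "if there is a clear benefit (or harm) from this medication, will terminate the study early and offer the medication to all patients".

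The only alpha is 0.05, in the power paragraph of Section 12, where it sizes the trial at 41 per group (82 in total, 90 to be recruited). That paragraph does not mention the look. The data analysis paragraph of Section 12 gives a t test for continuous measures and a covariance adjustment for demographic differences. It states no final significance level and names no test for comparing the two rates.

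**The concern.** Two descriptions of one look should agree on when it happens, what is tested and what stops the trial. These differ on all three, and neither refers to the other. Read alone, Section 13 would allow a stop on a criterion that nobody has defined. That matters more than usual here. Section 10 says that "it is impossible to blind the patients and researchers to the study assignment", and Section 22 has the principal investigator both operating and taking part in the data analysis. Section 22 also provides a departmental biostatistician who helps with the analysis and does not recruit, but it gives no independent party the stopping decision.

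The second matter is error control. An efficacy look at 0.01 uses part of the type I error. If the final test is then run at the full 0.05, the overall rate exceeds the design value by normal theory. By how much, and whether it does so in practice, depends on a test that the plan does not name.

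**Working it through.** **The two passages side by side**

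| | Section 9 | Section 13 |
|---|---|---|
| Trigger | half have had their procedures | half have completed the study |
| Outcome | voiding dysfunction rates | not stated |
| Criterion | p<0.01 for a difference | verbal, no number |
| Action | terminate | terminate and offer the drug; the wording follows both benefit and harm |

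**Gap between the triggers.** Section 8 states: "Participants will be enrolled in the study for approximately 6 weeks" and "We anticipate 2 years to enroll all the subjects into the study". With even accrual (an assumption) of 90 subjects over 104 weeks, 6 weeks brings in 6 × 90/104 = 5.2 subjects. If all outcomes available by then were used, the information fraction would be (45 + 5.2)/90 = 56% instead of 50%. The primary outcome is known on the day of surgery (Section 10, bladder challenge), so nothing is gained on it by waiting.

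**Overall error, normal theory.** The plan's own figure is 0.05, which is what a single final test at that level gives. With one look, the two z statistics are bivariate normal with correlation √t, where t is the information fraction, and

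overall error = 1 − P(|Z₁| < 2.576 and |Z₂| < c₂).

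- t = 0.50, final 0.05 (c₂ = 1.960): 5.46%. The look spends 1.00%, and trials rejecting only at the end contribute 4.46%.
- t = 0.56, final 0.05: 5.39%.
- t = 0.50, solved for 5.00% overall: final level 0.0452 (c₂ = 2.003). Rounded to 0.045 it gives 4.98%.

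**Overall error, exact binomial enumeration.** The look is at 21/20 then 41/41 (82 subjects), or 23/22 then 45/45 (90 subjects), with a common true rate of 10-28% and interim p<0.01.

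| Test and final level | 82 subjects | 90 subjects |
|---|---|---|
| Chi-square 0.05, no look | 4.99-5.89% | 5.34-5.92% |
| Chi-square 0.05, with look | 5.39-6.01% | 5.71-6.01% |
| Added by the look (points) | 0.12-0.40 | 0.09-0.45 |
| Chi-square 0.045, with look | 4.60-4.85% | 4.74-5.10% |
| Fisher's exact 0.05, with look | 1.84-3.30% | 2.14-3.19% |

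Chi-square is uncorrected throughout. Much of its excess over 5% is small-sample behaviour that is present with no look at all.

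**The test can decide the stop.** Take 10/23 v 2/22 at the look. Chi-square = 45 × (10×20 − 13×2)² / (12 × 33 × 23 × 22) = 45 × 30,276 / 200,376 = 6.80, so p = 0.0091 and the trial stops. Fisher's exact gives 0.0165 and the trial continues. This table is a chosen example: at 28% v 10%, the two tests disagree at the look in at most about 3% of trials.

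**Power at 28% v 10%** (the rates in the Background, with the look included)

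| Test and final level | 82 subjects | 90 subjects |
|---|---|---|
| Chi-square 0.05 | 57.3% | 61.9% |
| Chi-square 0.045 | 54.1% | 58.9% |
| Fisher's exact 0.05 | 47.2% | 49.6% |

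The stated 41 per group is taken as given here. Whether it is adequate is a separate question.

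**The case against.** The strongest reply is that there is only one rule. Section 9 fixes the outcome and the threshold. Section 13, in the same protocol, restates the same halfway look in plain language, and its mention of both benefit and harm fits a difference tested in either direction. On that reading a biostatistician applies p<0.01, the trigger discrepancy is about five subjects, and 5.46% becomes 5.39%. The interim level is already strict, the final 0.05 is inferred rather than stated, and with Fisher's exact no excess error arises.

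Most of this stands. A reader might infer that the plan leaves stopping to the investigators' judgement. That follows only if Section 13 is read apart from Section 9, and the documents do not require it. A reader might also infer that the plan intends the drug to be offered after a finding of harm. The preceding sentences of Section 13 concern withholding a possibly beneficial drug, so this is probably loose drafting.

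The reply does not explain why Section 13 uses a different trigger, and no text links it to Section 9. It also does not supply a final level or a test. The covariance adjustment in Section 12 does not fill that gap, because it is not stated to be the test of the two rates. If an adjusted analysis were meant as primary, the exact figures above would not apply to it directly.

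**Conclusion.** The point holds, at modest severity. As written, the two sections conflict on trigger and criterion and must be reconciled, and the only stated alpha ignores a planned efficacy look. With a final test at 0.05, the nominal excess is 0.46 points (5.46% v 5.00%). A reader might take the upper exact figure of 6.0% as the price of the look, but the look accounts for at most about 0.45 points of it. The difference in trigger barely matters for error.

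These figures assume two-sided testing, one look at 41 of 82 or 45 of 90 subjects, the same test at both looks, a true common rate between 10% and 28%, and a final level of 0.05, which the plan implies but does not state.

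**What to change.** 1. Have Section 13 refer to Section 9, so that the efficacy look has one trigger and one numeric criterion. Section 9's is the only rule with a number. If a review of complications at 6 weeks is also intended, describe it separately with its own timing.
2. Reconcile the benefit-or-harm sentence in Section 13 with Section 9, so that the consequence of each direction is unambiguous.
3. Name one test of the binary primary outcome and use it at both looks, keeping p<0.01 at the interim.
4. State the final two-sided level that suits the test: about 0.045 for chi-square or another normal-theory test. This holds 5% nominally; the worst exact value found is 5.10%, at 90 subjects.

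The text change is a few sentences. With chi-square, moving from 0.05 to 0.045 costs about 3 points of power at 28% v 10%: 57% to 54% with 82 subjects, 62% to 59% with 90. Fisher's exact at 0.05 needs no change of level, since its overall error is at most 3.3%, but it is not the free option that it may seem. Its power is 6.9 points (54.1 − 47.2) and 9.3 points (58.9 − 49.6) below chi-square at 0.045.
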